3.2. Secondary Endpoints

The following endpoints will be also evaluated as secondary endpoints:

- Rate of Major Adverse Event (MAE) Rate in hospital and at 30 days, 1, 2 and 3 years post-procedure, defined as a composite rate of cardiovascular death, index limb amputation and ischemia-driven Target Lesion Revascularization (TLR).
- Rate of occurrence of arterial thrombosis of the treated segment.
- Rate of ipsilateral embolic events of the study limb.
- Rate of clinically-driven target lesion revascularization at 6, 12, 24 and 36 months.
- Patency rate at 12 months post-procedure, defined as freedom from clinically driven TLR and duplex ultrasonography restenosis (ultrasound peak systolic velocity ratio ≤ 2.4 or stenosis ≤50%)
- Rate of vascular access site complication defined as the combined rate of hematoma, AV fistula or a pseudoaneurysm that required intervention, such as surgical repair or transfusion, prolonged hospital stay or required a new hospital admission.
- Lesion success (per device), defined as achievement of a final in-lesion residual diameter stenosis of <50% (by QA), using any device after wire passage through the lesion. Pre- and post-dilatation of the lesion with a non-study device is considered part of assigned device treatment.
- Technical success (per device), defined as achievement of a final in-lesion residual diameter stenosis of <50% (by QA), using the CVT Everolimus-coated PTA Catheter without a device malfunction after wire passage through the lesion. Preand post-dilatation are considered part of assigned device treatment.
- Clinical success (per subject), defined as technical success without the occurrence of major adverse events during the procedure.
- Procedural success (per subject), defined as lesion success without the occurrence of major adverse events during procedure.
- Ankle-Brachial Index (ABI) changes before procedure compared with ABI at discharge and at 6 and 12 months.

Confidential Page 16 of 79

- Change in WIQ (walking impairment questionnaire) from pre-intervention at 6 and 12-months follow-up.
- Change in walking distance from pre-procedure at 6 and 12 months.
- Change in Rutherford classification grades of chronic limb ischemia from preintervention at 6 and 12-months follow-up for the treated limb.

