3.6. Subject Exclusion Criteria

Subjects with any of the following criteria should be excluded:

- 1. Pregnant or lactating females.
- 2. Co-existing clinically significant aneurismal disease of the abdominal aorta, iliac or popliteal arteries.
- 3. Significant gastrointestinal bleeding or any coagulopathy that would contraindicate the use of anti-platelet therapy.
- 4. Known intolerance to study medications, everolimus or contrast agents.
- 5. Doubts in the willingness or capability of the subject to allow follow-up examinations.
- 6. Subject is actively participating in another investigational device or drug study.
- 7. History of hemorrhagic stroke within 3 months prior to treatment
- 8. Previous or planned surgical or interventional procedure within 30 days of index procedure.
- 9. Prior vascular surgery of the target lesion.
- 10. Lesion length is <3 cm or >15 cm or there is no normal proximal arterial segment in which duplex ultrasound velocity ratios can be measured.
- 11. Known inadequate distal outflow.
- 12. Significant inflow disease.
- 13. Acute or sub-acute thrombus in target vessel.
- 14. Use of adjunctive therapies (i.e. laser, atherectomy, cryoplasty, scoring/cutting balloons, brachytherapy, lithotripsy).
- 15. Outflow arteries (distal popliteal, anterior or posterior tibial or peroneal arteries) with significant lesions (≥ 50% stenosis) may not be treated during the same procedure.
- 16. Treatment of the contralateral limb during the same procedure or within 30 days of the study procedure.
- 17. Rutherford classification of 0, 1, 5 or 6.
- 18. Presence of prohibitive calcification that precludes adequate PTA treatment.
- 19. Subjects held in custody in an institution by official or court order.

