3.7. Subject Enrollment Point

All subjects who are candidates for endovascular treatment of the SFA or popliteal artery will undergo screening for study eligibility and, if applicable, for study

Confidential Page 18 of 79

enrollment. For any subject enrolled, a signature of informed consent will be obtained. The subject will be considered enrolled into the study upon the completion of all the following:

- A signed subject informed consent.
- Angiographic criteria for enrollment have been met.
- Successful treatment of the inflow (iliac) artery without complication, if applicable.
- Target lesion is successfully crossed by a guidewire.
- CVT Everolimus-coated PTA Catheter has entered the vasculature.

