4.3. SFA PTA Procedure

Procedural Medications

During the procedure, subjects will receive appropriate anticoagulation and other therapy according to standard hospital practice. The use of any medication for the treatment of vessel spasm, subject agitation or discomfort, hypotension, arrhythmias and hemodynamic changes during the procedure is at the discretion of the investigator.

Baseline Angiography

The diagnostic and interventional procedure can be conducted via either contralateral or antegrade approach at the investigator's discretion. A pelvic angiogram (digital subtraction angiography, Magnetic Resonance (MR) angiography, or Computed Tomography (CT) angiography) with run-off must have been performed prior to the PTA procedure (run-off should include popliteal and distal vessels) to confirm patent inflow and outflow as well as run-off required within the inclusion criteria.

Treatment Strategy

This study allows for treatment of *de novo* occluded/stenotic or re-occluded/restenotic superficial femoral (SFA) or popliteal artery (P1 segment) lesions in a single limb that are \geq 3 cm (30 mm) and \leq 15 cm (150 mm) in cumulative length, with up to two (2) CVT Everolimus-coated PTA Catheters. The lesion(s) should be within 1 cm distal to the femoral bifurcation in the SFA and 3 cm from the proximal margin of the intercondylar fossa.

The timing and method of treatment of any contralateral non-target lesion(s) is at the discretion of the investigator; however, it should be >30 days before or after the study procedure. A contralateral non-target lesion(s) cannot be treated during the same procedure in order to avoid complications.

Subjects selected for treatment must have a patent inflow artery and outflow arteries free from significant lesions (\geq 50% stenosis) as confirmed by angiography. If the ipsilateral iliac artery is diseased, but not occluded, it may be treated prior to the treatment of the target SFA/popliteal lesion. Successful treatment of the inflow artery is defined as attainment of final residual diameter stenosis of <30% without residual dissection or complication during the treatment. Outflow arteries (distal popliteal, anterior or posterior tibial or peroneal arteries) with significant lesions (\geq 50% stenosis) may not be treated during the same procedure.

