PROCEDURE/TEST	Prior to Procedure (Within 14 days)	Pre-Procedure (Within 24 hours)	PROCEDURE	Pre-Discharge	30 days (±7 days) Phone call or Office\hospital Visit	180 days (±30 days) Office/hospital visit	365 days (±30 days) Office /hospital visit	24 and 36 months (±30 days)
Patient Medical/Clinical History	√							
Chronic Concomitant Medications	✓			√	√	✓	✓	√
Patient Informed Consent	✓							
General/Inclusion Exclusion	√							
Angiographic/Anatomic Inclusion/Exclusion Criteria			✓					
Pregnancy Test (if applicable)	√							
Serum Hematology	✓			√ *				
Blood Chemistry	✓			√ *				
Peripheral Angiogram with Runoff		✓	✓					
Duplex Ultrasonography Examination	√ #			√		✓	✓	
Ankle Brachial Indices	✓			\checkmark		✓	✓	
Rutherford-Becker Classification	✓			✓		✓	✓	
WIQ	√					√	√	
Walking Test or Treadmill Test	✓					✓	✓	
Per-protocol Medications		√	✓	✓				
Adverse Events			√	√	✓	√	✓	✓

Confidential Page **27** of **79**

[#] optional * If the sub If the subject presents with less than desired clinical outcome or symptoms of an adverse event

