An approximation of the diameter of the vessel at the location of the target lesion. RVD is visually estimated during angiography by the Investigator and it is measured during QA by the Angiographic Core Laboratory.

Restenosis

Re-narrowing of the artery following the reduction of a previous narrowing. It is defined as the presence of a hemodynamically significant restenosis ($\geq 50\%$), as determined by angiography.

Rutherford/Becker Categories - Chronic Limb Ischemia

Category	Clinical Description	Objective Criteria
0	Asymptomatic, no hemodynamically significant occlusive disease	Normal results of treadmill*/stress test
1	Mild claudication	Treadmill* exercise complete, post exercise AP is greater than 50 mm Hg but more than 25 mm Hg less than normal
2	Moderate claudication	Symptoms between those of categories 1 and 3
3	Severe claudication	Treadmill* exercise cannot be completed post exercise AP is less than 50 mm Hg
4	Ischemic rest pain	Resting AP of 40 mm Hg or less, flat or barely pulsatile ankle or metatarsal plethysmographic tracing, toe pressure less than 30 mm Hg
5	Minor tissue loss, non-healing ulcer, or focal gangrene with diffuse pedal ischemia	Resting AP of 60 mm Hg or less, flat or barely pulsatile ankle metatarsal plethysmographic tracing flat or barely pulsatile, toe pressure less than 40 mm Hg
6	Major tissue loss, extending above transmetatarsal level, functional foot no longer salvageable	Same as category 5

^{*5} minutes at 3.2 km/h on a 12° incline

Worsening Rutherford Becker Clinical Category:

A deterioration (an increase) in the Rutherford Becker Clinical Category by more than 2 categories from the earliest post-procedural measurement or to a category 5 or 6.

Confidential Page 59 of 79

Revascularization

Target Lesion Revascularization (TLR):

Target lesion revascularization (TLR) is defined as any repeat percutaneous intervention of the target lesion or bypass surgery of the target vessel performed for restenosis or other complication of the target lesion.

Clinically Indicated (CI) Target Lesion Revascularization:

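### Ipsilateral iliac treatment in the index session follows the baseline and enters nine secondary change-from-baseline summaries, and section 6.4 does not separate the subjects who had it

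*Combined protocol and SAP*

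**What the plan says.** Section 4.3 (Treatment Strategy) permits inflow treatment: "If the ipsilateral iliac artery is diseased, but not occluded, it may be treated prior to the treatment of the target SFA/popliteal lesion". It defines success as "attainment of final residual diameter stenosis of <30% without residual dissection or complication during the treatment". Section 3.7 lists, among the items that complete enrolment, "Successful treatment of the inflow (iliac) artery without complication, if applicable", and Appendix B repeats this under Enrollment. Section 4.3 gives no interval between the iliac and target-lesion treatments.

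Two exclusions in section 3.6, repeated in the Protocol Summary, touch the same ground. Number 8 reads "Previous or planned surgical or interventional procedure within 30 days of index procedure" and number 12 reads "Significant inflow disease".

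In Table 2, baseline ABI, Rutherford category, WIQ and the walking or treadmill test all sit in the column headed "Prior to Procedure (Within 14 days" (closing bracket omitted). No repeat measurement is planned between iliac and target-lesion treatment. Section 3.2 makes the change in each measure a secondary endpoint; for ABI the wording is "Ankle-Brachial Index (ABI) changes before procedure compared with ABI at discharge and at 6 and 12 months".

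Section 6.2 removes from the evaluable population only subjects with a bail-out procedure or without a valid follow-up visit. Section 6.4 analyses the secondary endpoints descriptively, with no split or adjustment for iliac treatment.

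**The concern.** A successful iliac treatment improves inflow to the whole limb. It can be expected to raise ABI, WIQ score and walking distance and to lower the Rutherford category, whatever happens at the femoropopliteal lesion. If it takes place after baseline, its effect is counted in the change attributed to the study procedure. With no control arm, nothing offsets it.

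The protocol closes the comparable routes: exclusions 15 and 16 bar outflow and contralateral treatment in the same procedure. Iliac treatment is thus the one permitted second revascularisation of the study limb at the index session. A reader of the functional and haemodynamic results could not tell how much of the gain came from it.

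**Working it through.** The plan states no figure on this point. The check is of timing, scope and, under assumptions, size.

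**1. Which iliac treatments fall after baseline?** Inputs: exclusion 8 (30 days), Table 2 (baseline at most 14 days before the procedure), sections 4.3 and 3.7.

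| Iliac treatment | Allowed? | Relative to baseline | In the change score? |
|---|---|---|---|
| More than 30 days before index | Yes | Before | Its effect up to baseline is not |
| Staged, 30 days to 1 day before | No (exclusion 8) | – | – |
| Same session as index | Yes (4.3, 3.7) | After | Yes |

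The 14-day baseline window lies inside the 30-day bar, so same-session treatment is the permitted case that matters. For treatment more than 30 days earlier, the documents do not show whether walking measures have settled by baseline, but the treatment itself precedes it.

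**2. Which summaries are affected?** From section 3.2: ABI 3 (discharge, 6, 12 months) + Rutherford 2 + WIQ 2 + walking distance 2 = 9. Appendix B also defines ABI improvement from baseline: for a baseline below 0.9, either a rise of more than 0.10 or a follow-up value in the range 0.9-1.3. That definition carries the same effect.

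**3. Which are not affected by this route?** Worsening of Rutherford category is "A deterioration (an increase) in the Rutherford Becker Clinical Category by more than 2 categories from the earliest post-procedural measurement" or a move to category 5 or 6. Worsening of ABI is measured from the best early post-procedural value. Neither uses the pre-procedure baseline. The primary MAE and patency endpoints are not changes from baseline.

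**4. How large could it be?** Let f be the share of analysed subjects with same-session iliac treatment and d the mean added change per such subject. The shift in the mean change is f × d. The documents give neither quantity; the following are assumptions.

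- ABI, f = 5-20% and d = 0.10-0.20: from 0.05 × 0.10 = 0.005 to 0.20 × 0.20 = 0.040.
- Rutherford, f = 5-20% and d = one category: 0.05 to 0.20 category.
- WIQ and walking distance: 5-20% of whatever the per-subject iliac effect is.
- ABI improvement: only iliac-treated subjects can change status, so the proportion improved can rise by at most f.

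If no subject has same-session iliac treatment, every one of these is zero.

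**5. What does removing these subjects cost in precision?** Section 6.4 uses a Gaussian interval for a mean, so with equal SD the width ratio is 1/√(1 − f): 1/√0.95 = 1.026 to 1/√0.80 = 1.118. In whole subjects out of the roughly 68 evaluable in section 6.3, removing 3 gives √(68/65) = 1.023 and removing 14 gives √(68/54) = 1.122. The ABI set may be smaller than 68, because Appendix B drops values above 1.3, but the ratio depends only on the share removed.

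**The case against.** The strongest case against is that no stated decision rests on these endpoints. They are secondary and descriptive in a feasibility study, with no performance criterion or test attached. The size is wholly assumed, and even the upper illustrative ABI shift of 0.040 is below the 0.10 rise that counts as improvement in one subject. Removing iliac-treated subjects would also not yield a pure device effect, because section 4.3 requires pre-dilatation with a non-study balloon in everyone.

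Most of this stands and limits the weight of the point. The comparison with 0.10 does not: 0.040 is a mean diluted over all subjects, whereas a treated subject carries the full added gain, which could by itself move that subject across the threshold. Nor does the point need the device effect to be isolated; it asks only that a second revascularisation be visible.

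A reader might also infer that exclusions 8 and 12 contradict section 4.3 and reject patients it allows. The documents do not support that. Section 3.7 completes enrolment only after successful inflow treatment, and Table 2 places the angiographic criteria at the procedure. Appendix B's standard for good inflow is no lesion of 50% or more; an iliac artery brought below 30% residual stenosis meets it. Exclusions 15 and 16 name same-procedure treatment when they mean it, and exclusion 8 does not. The exemption is not written out, but the text can be reconciled.

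**Conclusion.** The point holds as a minor gap in the analysis plan. Same-session iliac treatment is permitted, follows baseline, and is not separated in sections 6.2 or 6.4. The nine change summaries, and ABI improvement if reported, can therefore include its effect, with an expected lean toward the device. The timing follows from the documents. The direction rests on the ordinary expectation that better inflow improves these measures. The size is unknown, and the figures above rest on assumed shares and effects.

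It would be tempting to extend this to the primary results. The documents do not support that by this route, since MAE and patency are not measured as changes from baseline.

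**What to change.** - In section 6.4, report the nine change summaries, and ABI improvement if it is reported, with and without subjects who had iliac treatment after baseline. Describe the second set as free of added iliac treatment, not as the effect of the device alone.
- Confirm that iliac treatment and its date are captured in the analysis data. Appendix M asks for every intervention step and device in the procedure log, but it is a core-laboratory instruction; the case report form is not reproduced in the document, so the field needs checking.
- As a clarification of wording only, state in exclusions 8 and 12, in both section 3.6 and the Protocol Summary, that non-occluded ipsilateral iliac disease successfully treated under section 4.3 in the same session is not excluded. The 30-day bar on staged treatment stays.

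The cost is nine extra descriptive rows (plus ABI improvement if used), a check of the data capture, and two short clauses in two places each. The extra rows would have intervals about 3-12% wider under the assumed 5-20% share. They would also describe subjects with less multilevel disease, a slightly different population, so they belong beside the full-set results and should not replace them.

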4.4. Post-Procedure Subject Management

Following the treatment procedure, the subject will be treated in accordance with the hospital standard of care for PTA interventions.

Sheath Removal and Ambulation

Use of approved vascular closure devices are allowed, provided the device is used according to the manufacturer's instructions for use and the operator has been properly trained in the device use. The subject may be ambulated according to hospital standards after hemostasis of the access site is achieved.

Medications

Confidential Page 23 of 79

The optimal duration of antiplatelet therapy for each subject is to be determined by the investigator.

All subjects enrolled into the trial are recommended to be maintained on 75 mg of clopidogrel bisulfate daily for a minimum of one (1) month following the angioplasty procedure, increased to three (3) months if a stent was used. All subjects will receive \geq 100 mg of aspirin daily to be taken throughout the length of the study following the procedure. (for minimum of 12 months following procedure)

If a subject develops hypersensitivity to clopidogrel bisulfate, they may be switched to ticlopidine hydrochloride at a dose in accordance with standard hospital practice.

NOTE: Subjects receiving ticlopidine hydrochloride must have a complete blood cell count (CBC) and differential blood count done per the IFU for ticlopidine hydrochloride.

4.5. Pre-Discharge Assessments

Medication History

The medication history should be updated as needed to include modifications to the chronic concomitant medications and protocol-required medications.

Clinical Assessments

The dorsalis pedis and posterior tibial pulses for the treated limb should be documented.

The distal ipsilateral extremity should be examined to ensure be examined to ensure no gangrene or ischemic ulcers are present.

Laboratory Tests

If the subject presents with less than desired clinical outcome or symptoms of an adverse event laboratory tests should be obtained within 12-24 hours post procedure (or prior to hospital discharge). Should laboratory tests be required, the following tests are recommended:

- Hemoglobin
- Hematocrit
- White Blood Cell Count and differential
- Absolute Platelet Count
- Blood Urea Nitrogen
- Serum Creatinine
- Serum Glutamic-Pyruvic Transaminase (SGPT)
- Serum Glutamic-Oxaloacetic Transaminase (SGOT)
- Coagulation tests as per standard of care of the hospital (e.g., Prothrombin Time (PT) and activated Prothrombin Time (aPTT)

Hemodynamic Evaluation

Confidential Page 24 of 79

An ankle brachial index (ABI) measurement will be obtained for the treated limb.

Duplex Ultrasonography Assessment/Rutherford Classification

Duplex ultrasound examination and Rutherford classification will be performed prior to hospital discharge of the treated limb in accordance with the ultrasound core laboratory requirements.

Adverse Events

Documentation of adverse events.

4.6. Subject Follow-up Post Hospital Discharge

Following hospital discharge, subjects will be followed at pre-determined time points during the study.

Subject Contact at 1 month $(30 \pm 7 \text{ days})$

Subjects will be contacted at 30 days post hospital discharge via phone call for assessment of overall condition and medications. Alternatively, this contact can be performed in a site visit.

Subject Clinical Visit at 6 months (180 ±30 days)

- Assessment of ischemia
- Claudication at rest and after walking
- Completion of the walking impairment questionnaire (WIQ)
- Completion of either the Walking Test or Treadmill Test
- Rutherford Classification
- Ankle Brachial Index (ABI) measured at rest.
- Data regarding any emergent treatment and or serious adverse events and/or need for repeat angiography or interventions and results of such, if applicable
- Concomitant medication (name, dose, duration)
- Duplex ultrasonography examination per core laboratory guidelines
- Adverse event assessment
- Medications

Subject Clinical Visit at 12 months (365 ±30 days)

- Assessment of ischemia
- Claudication at rest and after walking
- Completion of the walking impairment questionnaire (WIQ)
- Completion of either the Walking Test or Treadmill Test
- Rutherford Classification

Confidential Page 25 of 79

- Ankle Brachial Index (ABI), measured at rest
- Data regarding any emergent treatment and or serious adverse events and/or need for repeat angiography or interventions, and results of such if applicable
- Concomitant medication (name, dose, duration)
- Duplex ultrasonography examination
- Adverse event assessment
- Medications

Subject Phone call follow up at 24 Months (730 \pm 30 days)

Subjects will be contacted at 24 months post hospital discharge via phone call for assessment of overall condition and medications. Alternatively, this contact can be performed in clinical visit with the referring physician.

Subject Phone call follow up at 36 Months (1095 \pm 30 days)

Subjects will be contacted at 36 months post hospital discharge via phone call for assessment of overall condition and medications. Alternatively, this contact can be performed in clinical visit with the referring physician.

Confidential Page 26 of 79

Table 2. CVT-SFA Study Pre-Procedure, Procedural, Discharge and Follow Up Activities

Table 2. CV1-SFA Study Pre-Pro	ccaare,	110000		, 215011	arge and re	топ срт	ictivities	
PROCEDURE/TEST	Prior to Procedure (Within 14 days)	Pre-Procedure (Within 24 hours)	PROCEDURE	Pre-Discharge	30 days (±7 days) Phone call or Office\hospital Visit	180 days (±30 days) Office/hospital visit	365 days (±30 days) Office /hospital visit	24 and 36 months (±30 days)
Patient Medical/Clinical History	√							
Chronic Concomitant Medications	✓			√	√	✓	✓	√
Patient Informed Consent	✓							
General/Inclusion Exclusion	√							
Angiographic/Anatomic Inclusion/Exclusion Criteria			✓					
Pregnancy Test (if applicable)	√							
Serum Hematology	✓			√ *				
Blood Chemistry	✓			√ *				
Peripheral Angiogram with Runoff		✓	✓					
Duplex Ultrasonography Examination	√ #			√		✓	✓	
Ankle Brachial Indices	✓			\checkmark		✓	✓	
Rutherford-Becker Classification	✓			✓		✓	✓	
WIQ	√					√	√	
Walking Test or Treadmill Test	✓					✓	✓	
Per-protocol Medications		√	✓	✓				
Adverse Events			√	√	✓	√	✓	✓

Confidential Page **27** of **79**

[#] optional * If the sub If the subject presents with less than desired clinical outcome or symptoms of an adverse event

